14. STUDY MEDICATION COMPLIANCE

All administration of study treatment will be done at the clinic under supervision of the study staff; therefore, no formal analysis of compliance will be performed.

15. EFFICACY OUTCOMES

15.1. PRIMARY EFFICACY

15.1.1. PRIMARY EFFICACY VARIABLE(S) & DERIVATION(S)

The primary efficacy variable is peak FEV₁ (measured in first 4 hours after morning dosing). This will be measured after dosing on Day 3 and is collected on the Spirometry Study measurements eCRF page.

Three acceptable readings are performed at each of the timepoints in first 4 hours after morning dosing on Day 3 (5, 15 and 30 minutes and 1, 1.5, 2 and 4 hours) and the highest of the 3 is used for analysis purposes. Hence peak FEV_1 is derived as the highest of all these readings.

Document: Z:\RPL554\UYA25849\Biostatistics\Documentation\SAP\Verona RPL554-CO-204 SAP v1.0

Author: [name] Version Number: 1.0

Version Date: [18OCT2018]

Template No.: CS_TP_BS016 Revision 5 Reference: CS_WI_BS005

Effective Date: 01Apr2018

Page 27 of 50

Descriptive statistics (see Appendix 1 [Programming conventions for outputs]) for peak FEV_1 will be presented for all patients assigned to FAS, at each assessment and change from baseline at each assessment and overall (where overall is regardless of treatment period, day and timepoint to assess treatment group as a whole) as relevant. All summaries will be presented for each treatment group. In addition, a figure (bar graph) representing mean change from baseline FEV_1 to peak FEV_1 by treatment will be presented, including the standard error of the mean.

Change from baseline FEV₁ to peak FEV₁ (over 4 hours) at Day 3 will be derived to test the hypothesis described in section 15.1.3 with baseline defined as the FEV₁ pre-dose assessment (-5 minutes) collected on Day 1 of each treatment period. Peak FEV₁ at Day 3 is defined as the maximum post-dose value among the 5, 15, 30 minutes, 1, 1.5, 2 and 4-hour assessments collected at after morning dose on Day 3 of each treatment period.

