Prior/concomitant medications and therapies			Through	out the study	•	•
Adverse events				nout the study		

[a] Treatment Period 1 only

Table 4 Pre-dose and Post-dose Assessments on Each Day of Treatment Periods 1 to 3 in RPL554-CO-204

	Day 1												
Procedures	Pre- dose	0	5m	15m	30m	1h	1.25h	1.5h	2h	4h	6h	8h	12h [a]
Tiotropium/olodaterol dosing by Respimat®		X											
RPL554 or placebo dosing by nebulization		X											X
Brief physical examination	X												
Vital signs	X				X	X			X	X	X	X	X
12-lead ECG	X								X	X			
Spirometry	X[c]		X	X	X	X		X	X	X	X	X	X
Inhalation training	X												
Whole body plethysmography	X						X						
Randomization [b]	X												
Urine pregnancy test (females of childbearing potential)	X												
Dyspnea scale	X		X	X	X								
Adverse events					•		Throu	ıghout					•

Abbreviations: ECG=electrocardiogram; h=hours (post-dose); m=minutes (post-dose)

NOTE: Table 4 (Days 2 through 4) continues on next two pages.

Verona Pharma plc CONFIDENTIAL Page 32 of 66

[[]a] Post-dose measurements will be taken in relation to the morning dose of tiotropium/olodaterol and RPL554 or placebo. The 12-hour procedures will therefore be performed pre-dose before the evening dose of RPL554 or placebo

[[]b] Treatment Period 1 only

[[]c] Performed at 1 hour and immediately pre-dose

Due on during	Day 2														
Procedures	Pre-	0	15m	30m	1h	1.25h	2h	3h	4h	12h [a]					
Tiotropium/olodaterol dosing by Respimat®		X													
RPL554 or placebo dosing by nebulization		X								X					
Vital signs	X			X	X		X	X	X	X					
12-lead ECG	X						X								
Spirometry	X		X	X	X		X	X	X	X					
Adverse events	Throughout														

Abbreviations: ECG=electrocardiogram; h=hour; m=minutes

Verona Pharma plc CONFIDENTIAL Page 33 of 66

[[]a] Post-dose samples will be taken in relation to the morning dose of tiotropium/olodaterol and RPL554 or placebo. The 12-hour procedures will therefore be performed pre-dose before the evening dose of RPL554 or placebo.

Procedures		Day 3															Day 4 [a]				
	Pre-	0	5 m	15m	30m	45m	1h	1.25h	1.5h	2h	4h	6h	8h	8.25h	12h	12.25h	13 h	14h	16 h	23 h	24 h
Tiotropium/olodaterol dosing by Respimat®		X																			
RPL554 or placebo dosing by nebulization		X													X						
Brief physical examination																					X[b]
Vital signs	X				X		X			X	X	X	X								X
12-lead ECG	X									X											X
24-hour Holter monitor placed	X																				
Spirometry	X		X	X	X		X		X	X	X	X	X		X		X	X	X	X	X

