6.3.1.1 Pre-Dose Assessments

The following assessments will be performed prior to dosing:

- Confirm that respiratory medications were withheld as required
- Questioning for adverse events
- Urine pregnancy test (females of childbearing potential only)
- 12-lead ECG
- Dyspnea scale
- Vital signs
- Brief physical examination (see Section 7.4.5)
- Spirometry; 1 hour (±5 minutes) and immediately prior to study treatment administration
- Whole body plethysmography
- Inhalation training

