7.2 Efficacy/Pharmacodynamic Assessments

7.2.1 Pulmonary Function Tests

Spirometry (FEV₁ and FVC) will be performed at Screening, the end of study visit and the following time points in each treatment period:

- Day 1: 1 hour and immediately pre-dose; 5, 15 and 30 minutes and 1, 1.5, 2, 4, 6, 8 and 12 hours post-dose
- Day 2: pre-dose; 15 and 30 minutes and 1, 2, 3 4 hours and 12 hours post-dose
- Day 3: pre-dose; 5, 15 and 30 minutes and 1, 1.5, 2, 4, 6, 8, 12, 13, 14, 16, 23 and 24 hours post-dose.

Post-dose measurements will be taken in relation to the morning dose of tiotropium/olodaterol and RPL554 or placebo. The 12-hour measurement will therefore be taken pre-dose before the evening dose of RPL554 or placebo. The 24-hour measurement on Day 3 will be taken in the morning on Day 4 prior to discharge from the study center.

Spirometry assessments will be made in accordance with ATS/ERS guidelines (Miller et al, 2005). At all timepoints, three technically acceptable measurements should be made and recorded. Spirometry assessments may be performed up to eight times to obtain three acceptable readings. The highest FEV_1 and FVC readings from each assessment will be used for analysis even if the FEV_1 and FVC values come from two different forced exhalations.

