9.4.5 Efficacy/Pharmacodynamics

FEV₁ and FVC will be summarized as actual and change from baseline using descriptive statistics over time.

The peak effect on FEV_1 during these time intervals will be computed as the maximum value in the 4 hours after dosing. The average effect will be calculated as the AUC divided by the length of the time interval of interest. For analysis, the peak, average and trough FEV_1 will be divided by the pre-dose Day 1 baseline value.

Computed pharmacodynamic parameters for FEV_1 will be compared between the three study treatments using analysis of covariance (ANCOVA) models with fixed factors for treatment, period and patient, and using the pre-dose Day 1 baseline value as a covariate. FEV_1 will be analyzed using multiplicative models, which means that data (dependent and baseline) are logged prior to analysis and the result then transformed back to the linear scale giving treatment differences as ratios of geometric means.

Primarily the combination RPL554+tiotropium/olodaterol will be compared to tiotropium/olodaterol alone for each of the two doses of RPL554. Results of the comparisons will be expressed as the mean geometric ratio with 95% confidence intervals and associated, 2-sided, p-value.

Onset of action will be summarized by treatment and a Kaplan-Meier plot illustrating time to onset constructed.

Outcomes from the whole body plethysmography at 1.25 hours post-dose on Day 1 and 1.25, 8.25 and 12.25 hours post-dose on Day 3 will be compared in the same way as FEV₁ using multiplicative ANOVA models. The baseline of the visit (pre-first dose in a treatment period) will be used as covariate in these models.

The use of rescue medication during the study visits will be summarized by treatment, and, if appropriate, a Kaplan-Meier plot illustrating time to first use of rescue constructed.

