6.2. BASELINE

Baseline definitions are related to the treatment period the patient enters. For majority of endpoints (primary endpoint, relevant secondary/exploratory endpoints and safety endpoints assessed post-dose in the treatment periods), this will be the pre-dose assessment on Day 1 of each treatment period (treatment period 1 to treatment period 3). Baseline pre-dose FEV₁/FVC will be derived from 3 acceptable readings (performed up to 8 times to obtain these), with the highest being used for analysis. For safety laboratory tests (hematology, biochemistry, urinalysis) and 24-hour Holter monitoring screening assessment, performed 7 to 14 days before randomization, will be considered as baseline.

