15.1.3. PRIMARY ANALYSIS OF PRIMARY EFFICACY VARIABLE(S)

The primary efficacy objective of the study is to show that at least 1 RPL554 + tiotropium/olodaterol treatment group (RPL554 6mg + tiotropium/olodaterol and/or RPL554 1.5 mg + tiotropium/olodaterol) will increase peak FEV₁ (change from Baseline) compared to RPL554 placebo + tiotropium/olodaterol at Day 3 (measured in first 4 hours after morning dosing) by rejecting the null hypothesis described below at significance level α =0.05 level (2-sided):

$$H_0$$
: $\mu_i = \mu_0$ versus H_1 : $\mu_i \neq \mu_0$

where μ_j and μ_0 are the mean change from Baseline in peak FEV₁ at Day 3 (measured in first 4 hours after morning dosing) for 1 RPL554 + tiotropium/olodaterol treatment group (RPL554 6mg + tiotropium/olodaterol and/or RPL554 1.5 mg + tiotropium/olodaterol) and RPL554 placebo + tiotropium/olodaterol respectively.

Document: Z:\RPL554\UYA25849\Biostatistics\Documentation\SAP\Verona RPL554-CO-204 SAP v1.0

Author: [name] Version Number: 1.0

Version Date: [18OCT2018]

Template No.: CS_TP_BS016 Revision 5 Reference: CS_WI_BS005

Effective Date: 01Apr2018

Page 28 of 50

An ANCOVA will be used to test the hypothesis with change from baseline FEV₁ to peak FEV₁ (measured in first 4 hours after morning dosing) on Day 3 as response variable, and treatment, treatment period and baseline FEV₁ as covariates. Analyses will be implemented using the SAS® procedure MIXED as follows:

```
PROC MIXED DATA = ...;

CLASS SUBJECT PERIOD TREATMENT;

MODEL CHG = TREATMENT PERIOD BASELINE;

RANDOM USUBJID;

LSMEANS TREATMENT / CL DIFF;

RUN;

where CHG = difference in log (peak FEV1) - log (baseline FEV1) i.e. log (peak FEV1 / baseline FEV1)

TREATMENT = treatment group (1.5 mg RPL554, 6 mg RPL554 and placebo)

PERIOD = treatment period (treatment period 1, 2 and 3)

BASELINE = log (baseline FEV1)

USUBJID = subject ID
```

The primary comparison will be the contrast (difference in least squares mean [LSMEAN]) between 6 mg RPL554 and placebo on Day 3 (in first 4 hours after morning dosing).

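### Baseline FEV1 rests on the -5 minute reading alone; averaging it with the unused 1-hour pre-dose reading should modestly sharpen the FEV1 comparisons

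*SAP*

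**What the plan says.** Protocol 6.3.1.1 schedules Day 1 spirometry at "1 hour (±5 minutes) and immediately prior to study treatment administration". Section 7.2.1 repeats this ("Day 1: 1 hour and immediately pre-dose"), as does footnote c to Table 4 ("Performed at 1 hour and immediately pre-dose"). Both sessions take place in all three treatment periods.

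SAP 6.2 sets baseline for most endpoints in general terms: "this will be the pre-dose assessment on Day 1 of each treatment period", using the highest of three acceptable efforts. It does not say which of the two sessions is meant. SAP 15.1.1 does, for the primary endpoint: the FEV1 "pre-dose assessment (-5 minutes) collected on Day 1 of each" period. I take -5 minutes to be the protocol's immediate pre-dose session.

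Baseline enters the primary model twice. The response in SAP 15.1.3 is log(peak/baseline), and log baseline is also a covariate ("MODEL CHG = TREATMENT PERIOD BASELINE", with subject random). Protocol 9.4.5 divides peak, average and trough FEV1 by baseline and fits "fixed factors for treatment, period and patient, and using the pre-dose Day 1 baseline value as a covariate".

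No model or derived endpoint in either document uses the 1-hour reading. By contrast, the Day 4 trough (Protocol 9.3.2, SAP 15.2.1.1) is the mean of two readings an hour apart.

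**The concern.** In a crossover, the period baseline helps only by tracking how a patient's FEV1 in that period differs from his or her own average. Reading error weakens that tracking. Here a second untreated reading is taken an hour earlier under the same three-efforts rule (Protocol 7.2.1) and the same short-acting bronchodilator withhold (Protocol 5.9.1), and is then left out. Averaging it in should make the covariate more reliable and the confidence intervals slightly narrower for every FEV1 endpoint adjusted for this baseline, including the 1.5 mg comparison and the secondary endpoints. What is at stake is precision, not validity.

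**Working it through.** **1. The plan's own figure.** Inputs from Protocol 9.5: residual CV 6%, 70 patients, difference 5.1%, or about 50 mL on 1.3 L. From 9.4: two-sided 5%.

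- σ = √ln(1 + 0.06²) = 0.0599; SE of a pairwise contrast = σ√(2/70) = 0.01013.
- Power for 5.1%: ln(1.051)/0.01013 − 1.96 = 2.95, or 99.8%.
- Power for 50 mL on 1.3 L: ln(1.0385)/0.01013 − 1.96 = 1.76, or 96.1%.
- Difference detectable with 80% power: exp(2.80 × 0.01013) − 1 = 2.88%, about 37 mL.

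The stated 80% is not reproduced. That is a separate matter; here it shows only that power has room to spare.

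**2. Where baseline noise enters.** With b the log baseline and p the log peak, p − b = (treatment, period, patient) + βb is the same model as p = (treatment, period, patient) + (1 + β)b. The treatment contrast is identical. Dividing by baseline therefore adds no noise of its own; reading error acts only through the estimated covariate slope.

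**3. Gain with patient as a fixed effect (Protocol 9.4.5).** Let s_w be the SD of a patient's period-to-period state, s_m the error SD of one reading, c the correlation of that state between Day 1 and Day 3, and q the correlation of the two reading errors. The documents give none of these, so all are assumed. Apart from terms that averaging leaves unchanged, the residual variance contains

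c² · s_w² v / (s_w² + v), with v = s_m² for one reading and v = s_m²(1 + q)/2 for the mean of two.

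I take 6% as the residual CV with the single baseline, so the fall is the difference divided by 6² = 36. For s_w = 5% and s_m = 4% with q = 0: one reading 25 × 16/41 = 9.76; two readings 25 × 8/33 = 6.06; (9.76 − 6.06)/36 = 10.3% at c = 1.

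| s_w, s_m | q | c = 1 | c = 0.7 | c = 0.5 |
|---|---|---|---|---|
| 3%, 2% | 0 | 3.1% | 1.5% | 0.8% |
| 5%, 4% | 0 | 10.3% | 5.0% | 2.6% |
| 5%, 4% | 0.5 | 4.6% | 2.2% | 1.1% |
| 6%, 5% | 0 | 15.2% | 7.5% | 3.8% |

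A second parameterisation agrees. Let r be the within-patient correlation of one baseline reading with Day 3 peak, and ρ that of the two readings with each other. The variance ratio is (1 − 2r²/(1 + ρ))/(1 − r²). For r = 0.3-0.5 and ρ = 0.7-0.9 the fall is 0.5-6%.

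**4. Gain under the SAP's random-subject model.** The covariate slope there is partly set by differences between patients, so reading error carries more weight. Simulation with 70 patients over six sequences, between-patient SD 0.30, patient-specific response SD 0.10, s_w = 5% and residual SD 5-5.5% gave these approximate changes in contrast variance:

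| Error SD, 1-hour / -5 min | Share of Day 1 state present on Day 3 | SAP model | Protocol model |
|---|---|---|---|
| 3% / 3% | 0.9 | −10% | −7% |
| 3% / 3% | 0.5 | −8% | −2% |
| 3% / 3% | 0 | −3% | 0 |
| 1% / 1% | 0.5 | −1% | 0 |
| 7% / 3% | 0.5 | +8 to 9% | +2 to 3% |

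**5. Break-even.** With independent errors e₁ (1-hour) and e₂ (-5 minute), averaging helps when (e₁² + e₂²)/4 < e₂², that is, when e₁ < √3 e₂. If e₂ is 3%, e₁ must be below about 5.2%.

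**6. Consequence.** A 1-10% fall in variance narrows confidence intervals by 1 − √0.99 = 0.5% to 1 − √0.90 = 5%. At r = 0.5 and ρ = 0.7 (fall of 5.9%), power for 50 mL goes from 96.1% to 97.0% and the detectable difference from 2.88% to 2.79%.

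**The case against.** The best defence is that nothing here is wrong. A single pre-dose baseline is legitimate, SAP 15.1.1 only makes SAP 6.2 and Protocol 9.4.5 specific, and the reading nearest the dose is the natural choice. The primary peak comes about 48 hours and four blinded doses after baseline, so much of what a better Day 1 reading captures may have gone by then. Two sessions an hour apart may also share error. The change is not just one line either: the pre-dose value is also the time-0 point for the Day 1 AUC, the reference for onset of action and the basis of the ±20% period-entry check.

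Most of this stands, and it limits the point to a modest expected gain. It does not remove the point. The data are collected anyway, the plan already averages two readings an hour apart for trough, and nothing in the documents suggests that the 1-hour session is as much noisier as the break-even requires.

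A reader might infer that using baseline as both divisor and covariate lets its error in twice. Step 2 shows that it does not. A reader might also take the 10% case as a firm gain worth about 8 patients (70/0.897 = 78). That holds only with full persistence from Day 1 to Day 3, independent errors and the SDs chosen; relaxing either of the first two assumptions roughly halves it.

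**Conclusion.** The point holds as an efficiency suggestion. Averaging two similarly precise pre-dose readings is expected to lower contrast variance by roughly 1-10%, and more probably by a few percent. The figure rests on assumed repeatability and persistence, on 6% being the residual CV with the single baseline, and on the 1-hour error SD staying below about 1.7 times that of the immediate reading. It also assumes that the pre-dose schedule in the supplied protocol is the one in force.

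The documents do not support any reading that the current baseline is biased, that the SAP and protocol contradict each other on it, or that the trial is underpowered because of it.

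**What to change.** Before unblinding, amend SAP 6.2 and 15.1.1:

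- For the peak, average and trough FEV1 models, define each period's baseline as the mean of the 1-hour and immediate pre-dose FEV1, each being the highest of three acceptable efforts.
- If one of the two is missing, use the other.
- Keep the immediate pre-dose value as the time-0 point for the Day 1 AUC and as the reference for onset of action.
- Leave the ±20% period-entry check unchanged.

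The cost is a few lines of specification and programming, with no new measurement. The downside is slightly unequal baseline precision where only one reading is available.

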15.1.2. MISSING DATA METHODS FOR PRIMARY EFFICACY VARIABLE(S)

No imputation will be applied.

15.1.3. PRIMARY ANALYSIS OF PRIMARY EFFICACY VARIABLE(S)

The primary efficacy objective of the study is to show that at least 1 RPL554 + tiotropium/olodaterol treatment group (RPL554 6mg + tiotropium/olodaterol and/or RPL554 1.5 mg + tiotropium/olodaterol) will increase peak FEV₁ (change from Baseline) compared to RPL554 placebo + tiotropium/olodaterol at Day 3 (measured in first 4 hours after morning dosing) by rejecting the null hypothesis described below at significance level α =0.05 level (2-sided):

$$H_0$$
: $\mu_i = \mu_0$ versus H_1 : $\mu_i \neq \mu_0$

where μ_j and μ_0 are the mean change from Baseline in peak FEV₁ at Day 3 (measured in first 4 hours after morning dosing) for 1 RPL554 + tiotropium/olodaterol treatment group (RPL554 6mg + tiotropium/olodaterol and/or RPL554 1.5 mg + tiotropium/olodaterol) and RPL554 placebo + tiotropium/olodaterol respectively.

Document: Z:\RPL554\UYA25849\Biostatistics\Documentation\SAP\Verona RPL554-CO-204 SAP v1.0

Author: [name] Version Number: 1.0

Version Date: [18OCT2018]

Template No.: CS_TP_BS016 Revision 5 Reference: CS_WI_BS005

Effective Date: 01Apr2018

Page 28 of 50

An ANCOVA will be used to test the hypothesis with change from baseline FEV₁ to peak FEV₁ (measured in first 4 hours after morning dosing) on Day 3 as response variable, and treatment, treatment period and baseline FEV₁ as covariates. Analyses will be implemented using the SAS® procedure MIXED as follows:

```
PROC MIXED DATA = ...;

CLASS SUBJECT PERIOD TREATMENT;

MODEL CHG = TREATMENT PERIOD BASELINE;

RANDOM USUBJID;

LSMEANS TREATMENT / CL DIFF;

RUN;

where CHG = difference in log (peak FEV1) - log (baseline FEV1) i.e. log (peak FEV1 / baseline FEV1)

TREATMENT = treatment group (1.5 mg RPL554, 6 mg RPL554 and placebo)

PERIOD = treatment period (treatment period 1, 2 and 3)

BASELINE = log (baseline FEV1)

USUBJID = subject ID
```

The primary comparison will be the contrast (difference in least squares mean [LSMEAN]) between 6 mg RPL554 and placebo on Day 3 (in first 4 hours after morning dosing).

Peak FEV₁ and baseline FEV₁ will be log-transformed prior to analysis using natural logarithm. The difference between the two (log [peak FEV₁] – log [baseline FEV₁] equals log (peak FEV₁ / baseline FEV₁). The covariate, baseline FEV₁, will also be log transformed. Therefore, the LSMEAN statement between treatments in the above PROC MIXED will provide the log of the contrasts. Prior to presentations, the antilog of these point estimates and associated 95% confidence intervals will be performed, giving ratios of geometric means on the linear scale. The 2-sided p-value for the exponential (exp) least squares mean, exp(LSM), ratio between each of the 2 treatment groups and placebo will be reported.

Document: Z:\RPL554\UYA25849\Biostatistics\Documentation\SAP\Verona RPL554-CO-204 SAP v1.0

Author: [name] Version Number: 1.0

Version Date: [18OCT2018]

Template No.: CS_TP_BS016 Revision 5 Reference: CS_WI_BS005

Effective Date: 01Apr2018

Page 29 of 50

Summary statistics for FEV₁ will be presented for baseline, peak on Day 3 (in first 4 hours after morning dosing) and change from baseline to peak by treatment group on patients with both assessments, on the original scale.

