Duration of Treatment:	The approximate planned duration of participation for each patient will be up to 61 days: 7 to 14-day screening period, up to 9 days treatment (three treatment periods of 3 days each separated by 7 to 14 days) and an end of study visit 4 to 10 days after the last treatment visit (Day 4 of Treatment Period 3).
Statistical Methods:	Treatments will be compared using analysis of covariance adjusting for treatment, period, patient and baseline. Multiplicative models will be used for FEV ₁ and outcome from whole body plethysmography and additive models for blood pressure, pulse rate and ECG heart rate. RPL554 doses will first be compared to placebo using a closed test procedure starting with the highest dose of RPL554.
Sample Size:	This is a complete block three-way crossover study. Assuming a residual coefficient of variation of 6% for peak FEV ₁ , 70 patients will give an 80% power to detect a pairwise difference in FEV ₁ of 50 mL.

Verona Pharma plc CONFIDENTIAL Page 8 of 66

TABLE OF CONTENTS AND LIST OF TABLES AND FIGURES

Table of Contents

SPC	NSOI	R SIGNA	ATURE PAGE	2
INV	ESTI	GATOR	SIGNATURE PAGE	3
COl	NFIDE	ENTIAL	ITY STATEMENT	3
COl	NTAC	T LIST .		4
DET	TAIL (OF AME	ENDMENTS SINCE THE PREVIOUS VERSION	5
SYN	IOPSI	S		6
TAE	BLE O	F CONT	TENTS AND LIST OF TABLES AND FIGURES	9
	Tabl	e of Cor	ntents	9
	List	of Table	es and Figures	12
LIS	ΓOF	ABBRE	VIATIONS AND DEFINITION OF TERMS	13
1	INT	RODUC	TION	14
	1.1	Diseas	e and Study Medication Review	14
	1.2	Summ	ary of Risks and Benefits	16
2	OBJ	ECTIVE	ES	17
	2.1	Primar	y Objective	17
	2.2	Second	dary Objectives	17
	2.3	Explor	ratory Objectives	17
3	INV	ESTIGA	ATIONAL PLAN	18
	3.1	Overal	1 Study Design and Plan Description	18
	3.2	Discus	sion of Study Design, including the Choice of Control Groups	19
	3.3	Planne	d Duration of the Study	19
	3.4	Definit	tion of the End of the Study	19
4	SEL	ECTION	N OF STUDY POPULATION	20
	4.1	Inclusi	on Criteria	20
	4.2	Exclus	ion Criteria	21
	4.3	Remov	val of Patients from Therapy or Assessment	22
		4.3.1	Study Treatment Discontinuation	22
		4.3.2	Patient Withdrawal	22
		4.3.3	Study Discontinuation	23
		4.3.4	Replacement Policy	23
5	STU	DY TRI	EATMENTS	24
	5.1	Study '	Treatments Administered	24
	5.2	Identit	y of Study Treatments	24
		5.2.1	RPL554 and Placebo	24
		5.2.2	Tiotropium/olodaterol Respimat®	24
	5.3	Prepara	ation and Labelling	25
		5.3.1	Nebulized RPL554 and Placebo	25
		5.3.2	Tiotropium/olodaterol	25

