3. STUDY DESIGN

3.1. GENERAL DESCRIPTION

This is a Phase II, randomized, double blind, placebo controlled, complete block three-way crossover study to

Document: Z:\RPL554\UYA25849\Biostatistics\Documentation\SAP\Verona RPL554-CO-204 SAP v1.0

Author: [name] Version Number: 1.0

Version Date: [18OCT2018]

Template No.: CS_TP_BS016 Revision 5 Reference: CS_WI_BS005

Effective Date: 01Apr2018

Page 11 of 50

investigate treatment with nebulized RPL554 and tiotropium/olodaterol Respirat® in patients with moderate to severe chronic obstructive pulmonary disease (COPD).

A total of approximately 70 male or female COPD patients (as defined by the American Thoracic Society [ATS]/European Respiratory Society [ERS] guidelines with symptoms compatible with COPD for at least 1 year prior to Screening) aged 40 to 80 years (inclusive) will be randomized across up to 4 sites, in the Unites States (US) and the United Kingdom (UK). All patients will receive 3 combinations of study treatment (1.5 mg RPL554, 6 mg RPL554 and placebo) in a randomized, crossover design; therefore, each patient will act as his or her own control in the study. There are 6 possible treatment sequences a patient can be randomized to: a) RPL544 1.5 mg / RPL544 6.0 mg/Placebo, b) RPL544 1.5 mg / Placebo / RPL544 6.0 mg, c) RPL544 6.0 mg / RPL544 1.5 mg / Placebo, d) RPL544 6.0 mg / RPL544 1.5 mg, e) Placebo / RPL544 1.5 mg / RPL544 6.0 mg and f) Placebo / RPL544 6.0 mg / RPL544 1.5 mg, with the ratio of patients to treatment groups / treatment sequences being 1:1:1:1:1:1.

Patients will be screened for eligibility, including a reversibility test with salbutamol (in UK) or albuterol (in US) and ipratropium between 7 and 14 days before the first dose of study treatment. Eligible patients will then attend 3 separate treatment periods (Treatment periods 1 to 3), with each lasting 3 days and separated by a 7 to 14-day washout period. Figure 1 below summarizes these details.

Document: Z:\RPL554\UYA25849\Biostatistics\Documentation\SAP\Verona RPL554-CO-204 SAP v1.0

Author: [name] Version Number: 1.0

[figure not shown]
Version Date: [18OCT2018]

Template No.: CS_TP_BS016 Revision 5 Reference: CS_WI_BS005

Effective Date: 01Apr2018

Figure 1 Study Flow Chart

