7. STATISTICAL CONSIDERATIONS

7.1. ADJUSTMENTS FOR COVARIATES AND FACTORS TO BE INCLUDED IN ANALYSES

The following covariates are used in the analyses. For details of their inclusion in the models, see the specific analysis section.

- Randomized treatment (fixed).
 - RPL554 1.5mg
 - o RPL554 6.0mg
 - Placebo

Document: Z:\RPL554\UYA25849\Biostatistics\Documentation\SAP\Verona RPL554-CO-204 SAP v1.0

Author: [name] Version Number: 1.0

Version Date: [18OCT2018]

Template No.: CS_TP_BS016 Revision 5 Reference: CS_WI_BS005

Effective Date: 01Apr2018

Page 19 of 50

- Treatment period (fixed).
 - o Treatment period 1
 - o Treatment period 2
 - Treatment period 3
- Baseline value of analyzed variable (covariate).

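### As printed, the SAP's primary model fits no patient effect: the ID named in RANDOM is not in CLASS, and the model text does not name patient

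*SAP*

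**What the plan says.** SAP 15.1.3 gives the primary analysis as a sentence and as code.

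- **Code.** The CLASS statement is "CLASS SUBJECT PERIOD TREATMENT", the MODEL statement has treatment, period and baseline, and the last effect is "RANDOM USUBJID". The legend states "USUBJID = subject ID" and has no entry for `SUBJECT`.
- **Sentence.** The change from baseline to peak FEV1 is taken "as response variable, and treatment, treatment period and baseline" FEV1 as the covariates. Patient is not mentioned.
- **SAP 7.1.** The list of model terms has randomized treatment, treatment period and, as its last entry, the baseline value of the analyzed variable. It refers to the analysis sections for detail.
- **SAP 3.1.** The design is a three-way crossover; "therefore, each patient will act as his or her own control in the study".

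The supplied protocol does include patient. The synopsis says "Treatments will be compared using analysis of covariance adjusting for treatment, period, patient and baseline", and section 9.4.5 specifies "models with fixed factors for treatment, period and patient, and using the pre-dose Day 1 baseline value as a covariate". SAP 3.3 declares no change from the protocol. However, SAP section 1 says it is based on protocol version 2.0, whereas the supplied protocol describes itself as the first version.

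**The concern.** PROC MIXED treats any variable outside CLASS as continuous. `RANDOM USUBJID` therefore cannot give each patient an intercept unless `USUBJID` is in CLASS, and listing `SUBJECT` there does nothing because no effect uses it. A programmer who turns to the text to resolve the conflict finds a model with three terms and no patient.

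A crossover gains its precision by removing differences between patients from the error. The 6% in protocol 9.5 is a residual CV for a complete-block crossover, so the sample-size reasoning presupposes a patient term. Without one, between-patient variation in the response is counted as error. The same model serves secondary variables 1 to 5 and 7 (SAP 15.2.3.1) and AUC0-24h FEV1 (SAP 15.3.3), so the slip reaches most of the inferential lung-function results.

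**Working it through.** **What the printed code does**

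| ID supplied as | Result |
|---|---|
| Character (protocol 5.7 uses the form XXX-YYY) | Step stops with an error; no result |
| Numeric | One random coefficient on the ID number, shared by all patients; no patient intercept |
| RANDOM line dropped and model built from the text | Runs with treatment, period and baseline only |

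Only the last two lose the patient term silently. The figures below apply only to them.

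**Inputs from protocol 9.5:** 70 patients, residual CV 6%, and two statements of the effect (5.1%, and about 50 mL on 1.3 L). Alpha is 0.05 two-sided.

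**The plan's own figure, with patient fitted**

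- Residual log SD = √ln(1 + 0.06²) = 0.05995.
- SE of a pairwise contrast = 0.05995 × √(2/70) = 0.01013.
- 50 mL: ln(1.35/1.30) = 0.03774; 0.03774/0.01013 = 3.72; power 96% (noncentral t, 135 df).
- 5.1%: ln(1.051) = 0.04974; 0.04974/0.01013 = 4.91; power 99.8%.

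Protocol 9.5 states 80%. That does not reproduce under the within-patient formula, and 5.1% of 1.3 L is 66 mL, not 50 mL. This is a separate matter; here 96% and 99.8% serve only as reference values.

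**Without a patient term, complete data**

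Each patient receives all three treatments, so the patient effect cancels from the contrast and the true SD of the estimate stays about 0.01013. The model, however, reports an SE larger by the factor r = √(1 + (s/0.05995)²), where s is the SD of the patient effect on log(peak/baseline). Neither document gives s, so a range is assumed. With the t quantile 1.972 (204 df), power is approximately Φ(effect/0.01013 − 1.972 r).

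For s = 0.10: r = 1.945 and 1.972 × 1.945 = 3.835. For 50 mL, Φ(3.725 − 3.835) = Φ(−0.110) = 46%.

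| Assumed s | r | Type I error | Power, 50 mL | Power, 5.1% |
|---|---|---|---|---|
| Patient fitted | 1 | 5% | 96% | 99.8% |
| 0.03 | 1.12 | 2.7% | 94% | 99.7% |
| 0.05 | 1.30 | 1.0% | 88% | 99% |
| 0.10 | 1.95 | 0.01% | 46% | 86% |
| 0.15 | 2.69 | < 0.01% | 6% | 34% |

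Simulation of 70 patients over six sequences (4000 replicates, period and baseline in the model) gives 94%, 88%, 45% and 7% for 50 mL, in agreement. Entering a numeric ID as a single continuous term recovers nothing: 88% and 46% at s = 0.05 and 0.10.

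**The case against.** The strongest reply is that this is a one-word naming slip whose intent is plain. The legend identifies `USUBJID` as the subject ID, a RANDOM statement on it can only mean a patient effect, and 15.1.3 makes the code part of the specification. SAP 7.1 lists fixed terms and a covariate and defers to the analysis section, so omitting a random effect there is incomplete wording and does not show that patient was dropped. With IDs in the protocol's format the step would fail visibly and be corrected before any result existed.

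Most of this stands. A reader might infer that the trial will be analyzed without a patient effect and will lose its power. The documents do not support that: the intended model is evident, and the loss needs a numeric ID or a discarded RANDOM line. The size also depends on an SD in neither document and on the effect chosen. As context only, protocol 1.1 reports 103 mL for the 1.5 mg dose added to tiotropium alone. On an assumed 1.3 L, even s = 0.15 would leave power above 98%: ln(1.403/1.300)/0.01013 = 7.52, and Φ(7.52 − 5.31) = 98.6%.

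What the reply does not remove is that the printed specification cannot be run as intended, and that its words, read alone, describe a different model.

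**Conclusion.** The point holds and should be fixed. As printed, the primary model contains no working patient term, and neither the 15.1.3 sentence nor SAP 7.1 supplies one. The consequence is either a visible failure or, in the silent case, an overstated SE. The silent error is conservative: with complete data the estimate is not biased and type I error falls. The power figures are conditional on that case, on the assumed patient SD and on the 6% CV.

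Two stronger readings are not supported.

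- **That a random patient intercept is itself wrong.** Correctly coded, it is a legitimate model and does not inflate type I error. It loses precision against fixed patient only if the baseline slopes within and between patients differ, which the documents do not show.
- **That the SAP departs from its governing protocol without saying so.** Fixed patient is established only for the supplied protocol. The SAP follows version 2.0, which is not available here.

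**What to change.** 1. Use one identifier throughout and list it: `CLASS USUBJID PERIOD TREATMENT;`. With the existing RANDOM statement this fits the intended patient intercept.
2. Name patient in the 15.1.3 sentence and in SAP 7.1, stating whether it is fixed or random. The correction then carries to secondary variables 1 to 5 and 7 and to AUC0-24h.
3. Before unblinding, check whether protocol version 2.0 specifies patient as fixed or random, and fit what it specifies. If random patient is kept against a protocol that says fixed, record the change in SAP 3.3.

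Either patient model is acceptable, and no further covariate, such as the patient's mean baseline, is needed. The cost is a few words of SAP text and code and one check against version 2.0; no new data are required.
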